## 5.0 DATA COLLECTION AND RETENTION

The study endpoints data will be collected from each participant's study questionnaires. The data will be collected electronically via the patient's own device, and uploaded to an electronic data capture system. Only patient data from the stratified indication(s) will be used for analysis of symptom response. The data will be used to demonstrate that the Nu-V3 device provides participants with relief of the symptoms of pain, depression, anxiety and/or sleeplessness. The data analysis will include comparative data for each participant's questionnaire prior to beginning treatment with the Nu-V3 device, the participant's weekly questionnaires during

treatment and the questionnaire completed at the end of the treatment with the Nu-V3 device.

Interim analyses of available data will be regularly submitted to the FDA for review.

The Principal Investigator at each site will be responsible for recording, collecting, and storing the research participant's study data. The written records must be stored in a secure location. Only the Principal Investigator or designated study staff will have access to the study records and all electronic files will be password protected. The Principal Investigator will also maintain adequate records for the study including:

- all correspondence with the IRB and Sponsor
- other pertinent data related to the study

All records are to be retained by the Principal Investigator for a period of seven (7) years following the closure of the study. Following study closure, the Principal Investigator shall inform Nu-Life of the location of study records and storage changes (i.e. the Principal Investigator leaves the institution where the study was conducted). In such cases, the study records may be transferred to another institution, investigator, or to Nu-Life upon written agreement between the Principal Investigator and Nu-Life.

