## 4.0 STUDY PROTOCOL

The Nu-V3 Clinical Study is a prospective, single-arm, open-label, multi-center study using the Nu-V3 cranial nerve stimulation treatment device in patients with pain, anxiety, depression, and/or sleeplessness.

For this Phase I study, a total of 50-100 patients at multiple centers will be registered for study participation. Study participants are those who have signed the informed consent form, met the inclusion and exclusion criteria, and are enrolled in the study at one of multiple sites. Enrolled participants are stratified based on their pain, anxiety, depression, and/or sleeplessness symptom presentation at baseline and treated with the Nu-V3 device for 8 weeks, then observed for an additional 4 weeks. Interim analysis of reported data will be based on baseline stratifications and conducted at 4, 8, and 12 weeks during this time. Post study, participants will be given the chance to continue with an optional maintenance treatment with the Nu-V3 device per a 2-weeks on, 2-weeks off schedule, for an additional 12 weeks, with an 8-week observation.

Subjects enrolled onto the Nu-V3 Clinical Trial will undergo the following regimen:

- At the baseline visit, patients will be asked to complete study questionnaires (Appendix 11) regarding all of the following symptoms: pain, anxiety, depression, and/or sleeplessness, as well as their quality of life, active medications, medical history, and demographical information.
- At each subsequent visit, patients will be asked to complete study questionnaires regarding all the following symptoms: pain, anxiety, depression, and/or sleeplessness, as well as their activity level and quality of life.
- The sessions will begin with the Nu-V3 device being placed on the left ear and three small pads (non-invasive) being placed on the ear. Each Nu-V3 device

lasts for up to 14 days with a change in the pads approximately 7 days into the treatment.

- Each session takes approximately 15-20 minutes. The placement of the device takes approximately 5 minutes and the remaining time is spent verifying ePRO form completion, and evaluating the patient for all device effects.
- The Nu-V3 device is mobile and is worn externally on the left ear 24 hours a day during treatment, fitting comfortably behind the ear. An electrical signal is sent to the external ear through coated wire leads attached to the device and adhesive pads which attach to three sites on the ear.

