1. Inclusion/Exclusion, Registration, Medications, Treatment forms to be completed by site coordinator via online module.
2. Patient Onboarding and Orientation includes introductory demographics form, Nu-V3 patient training video
3. ePRO questionnaires completed on patient's mobile device: DQ-9 (baseline), PTB-7, PEG, GAD-7, PHQ-9, PROMIS 4a, PGIC
4. If patient consents to media testimony, site will collect via study collection process every 4 weeks.

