## 4.2 Protocol Deviations

In the event the Nu-V3 device is inadvertently removed or the device comes off, the participant will contact the Principal Investigator. The Principal Investigator will determine the appropriate course of action to be taken.

If the study participant is unable to wear the device on their left ear, the study participant will be allowed to wear the device on their right ear, which will result in a minor study deviation. Left-ear deviations could be due to discomfort, sleep position, pain at the local site, or infection. A lack of significant improvement by the end of week 4, per the Principal Investigator's discretion, can also result in a deviation from left-ear placement.

Device placement should be recorded on the study treatment form within the electronic data capture system.

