## 8.0 STUDY ENDPOINT and DATA ANALYSIS

### 8.1 Primary Endpoints: Primary endpoints consisted of the following:

Safety: The primary safety endpoint is the occurrence of reported unanticipated problems involving risk to subjects or others (“UPIRTSOs”). These UPIRTSOs are defined as those problems which alter the risks to subjects or others. This includes any study suspensions or holds. The primary safety endpoint analyses will be based on a risk-benefit conclusion.

Effectiveness: The primary effectiveness endpoints are an overall change in median reported symptoms of pain, anxiety, depression, and/or sleeplessness via numeric rating scales at 8 weeks. This primary effectiveness is measured by median reported symptom changes in pain, anxiety, depression, and/or sleeplessness for respective stratified populations via the following validated tools: Pain - Pain Intensity and Interference (PEG\_Scale), Anxiety - Generalized Anxiety Disorder 7-item (GAD-7) scale, Depression - Patient Health Questionnaire (PHQ-9), Sleeplessness - PROMIS short form 4a, and overall improvement of quality of life (QOL) - Patient’s Global Impression of Change (PGIC).

The hypothesis-driven criterion of effectiveness is to show that there is a statistically significant reduction in the median reported pain, anxiety, depression, and/or sleeplessness levels of patients using the Nu-V3 device. The second criterion is intended to show that there is a statistically significant improvement in reported quality of life and perceived treatment benefit, secondary to overall reported symptom reductions of pain, anxiety, depression, and/or sleeplessness.

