Primary Endpoints: Primary endpoints consisted of the following:

1. **Safety:** The primary safety endpoint was the occurrence of reported unanticipated problems involving risk to subjects or others (“UPIRTSOs”). These UPIRTSOs are defined as those problems which alter the risks to subjects or others. This includes any study suspensions or holds. The primary safety endpoint analyses were based on a risk-benefit conclusion.
2. **Effectiveness:** The primary effectiveness endpoints were overall reduction in median reported symptoms of pain, anxiety, depression, and/or sleeplessness via numeric rating scales at 8 weeks. This primary effectiveness is measured by median reported symptom reductions in pain, anxiety, depression, and/or sleeplessness via the following validated tools: Pain intensity and interference- PEG Scale, Anxiety- Generalized Anxiety Disorder 7-item (GAD-7) scale, Depression- Patient Health Questionnaire (PHQ-9), Sleeplessness- PROMIS short form 4a, and overall improvement of quality of life (QOL) - Patient’s Global Impression of Change (PGIC).

The patient’s perceived treatment benefit and device comfort information, will be captured via the non-validated tool, Perceived Treatment Benefit Form (PTB-7). This effectiveness tool will measure median levels of reported perceived treatment benefit and device comfort.

The hypothesis-driven criterion of effectiveness was to show that there was a statistically significant reduction in the median reported pain, anxiety, depression, and/or sleeplessness levels of patients using the Nu-V3 device. The second criterion was intended to show that there was a statistically significant improvement in reported quality of life and perceived treatment benefit secondary to overall reported symptom reduction of pain, anxiety, depression, and/or sleeplessness.

Secondary Endpoints: Secondary endpoints consisted of the following:

1. **Effectiveness:** The secondary effectiveness endpoint was overall reduction in median reported symptoms of pain, anxiety, depression, and/or sleeplessness via numeric rating scales at 4, 8, and 12 weeks. This was measured via the following validated tools: Pain intensity and interference- PEG Scale, Anxiety- Generalized Anxiety Disorder 7-item (GAD-7) scale, Depression- Patient Health Questionnaire (PHQ-9), Sleeplessness- PROMIS short form 4a, and overall improvement of quality of life- Patient’s Global Impression of Change (PGIC).

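### Symptom scores outside a participant's entry indication(s) are collected but enter no planned analysis under the Protocol, so non-entry worsening reaches the safety conclusion only by discretionary report

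*Protocol*

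**What the plan says.** **Collection.** Protocol section 4.0: "At each subsequent visit, patients will be asked to complete study questionnaires regarding all the following symptoms: pain, anxiety, depression, and/or sleeplessness". The footnote to the section 4.1 assessment table lists the packet: "ePRO questionnaires completed on patient's mobile device: DQ-9 (baseline), PTB-7, PEG, GAD-7, PHQ-9, PROMIS 4a, PGIC". No instrument is reserved for participants who entered with the matching symptom.

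**Stratification.** Section 4.0: "Enrolled participants are stratified based on their pain, anxiety, depression, and/or sleeplessness symptom presentation at baseline". A participant may belong to more than one stratum. No score threshold is given.

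**Restriction.** Section 5.0: "Only patient data from the stratified indication(s) will be used for analysis of symptom response". Sections 8.1 and 8.2 likewise tie the primary and secondary effectiveness endpoints to the matching stratum.

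**SAP.** The SAP's endpoint paragraph follows Protocol section 5.0 closely but leaves that sentence out. Its primary effectiveness endpoint is "overall reduction in median reported symptoms of pain, anxiety, depression, and/or sleeplessness", with no mention of strata.

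**Safety.** Protocol section 8.1: "The primary safety endpoint is the occurrence of reported unanticipated problems involving risk to subjects or others", to be analysed through a risk-benefit conclusion. SAP Table 4.1 and SAP Section 5.0 (Results) count reported events of this kind in all registered patients. Neither document plans a shift table or a count of participants who worsen, and neither names a score that leads to a report.

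**The concern.** Limiting the effectiveness analysis to the symptom a participant came in with is reasonable. But the same scales are also the only systematic record of whether another of the four symptoms appears or gets worse during treatment, and no planned safety analysis uses them for that.

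The risk-benefit conclusion would therefore draw on unequal evidence. Benefit is measured weekly on validated scales. Deterioration in a non-entry domain counts only if a participant mentions it, or staff notice it, and someone judges it reportable. Followed as written, the Protocol could not say whether relief of one target symptom comes with worsening of another, although the data to describe this would be in the database. The question is a natural one for a device worn on the ear around the clock, with sleep among its four targets.

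**Working it through.** The plan states no figure on this point, so there is nothing to reproduce. The check traces each source of symptom data to its planned use, then counts.

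**1. Where could non-entry worsening be counted?**

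| Source | Planned use | Shows non-entry worsening? |
|---|---|---|
| PEG, GAD-7, PHQ-9, PROMIS 4a (Protocol) | Median change within stratum | No |
| Same scales (SAP) | Median reduction, strata not mentioned | Only through a group median |
| PGIC (Appendix 11) | Quality-of-life endpoint | No: the lowest category covers both no change and worsening |
| PTB-7 item 4 (0-10 rating of all four symptoms) | No analysis of this item described | No |
| PTB-7 items on benefit and comfort | Medians, sub-analyses | No |
| Evaluation of device effects at each session (section 4.0) | No endpoint or table | No |
| Unanticipated-problem form (section 7.0, Appendix 7) | SAP Table 4.1 | Yes, if someone files it |

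The last row is the one route to a safety count. It depends on judgement and is tied to no score.

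**2. Scores unused under the Protocol.** Week 1 is the baseline packet and cannot show worsening. Weekly packets at Weeks 2 to 12 give 11 post-baseline packets (reading the combined Week 9-11 column as three, as the weekly schedule implies).

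- Scores per participant: 11 x 4 = 44.
- One entry symptom: 11 x 3 = 33 unused.
- Two: 11 x 2 = 22. Three: 11 x 1 = 11. Four: 0.

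If Weeks 9-11 yielded a single packet there would be 9 packets, and 9 x 3 = 27 of 9 x 4 = 36 unused, the same three quarters.

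**3. Does the SAP's pooled median close the gap?** Suppose 60% improve by 4 points and 40% worsen by 4. With 50 participants, 30 have a change of -4 and 20 of +4. The 25th and 26th ordered values are both -4, so the median change is -4 and the 20 who worsened do not show in it.

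**4. Illustration of scale (assumed rates; the documents give none).** Let 25% to 50% of participants lack a given symptom at entry, and 5% to 20% of those develop it. With m participants outside the stratum and rate r, expected cases are m x r and the chance of at least one is 1 - (1 - r)^m.

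- N = 50: m = 12 (12.5 rounded down) to 25. Expected cases run from 12 x 0.05 = 0.6 to 25 x 0.20 = 5. The chance of at least one runs from 1 - 0.95^12 = 0.46 to 1 - 0.80^25 = 0.996.
- N = 100: m = 25 to 50. Expected cases run from 1.25 to 10. The chance of at least one runs from 1 - 0.95^25 = 0.72 to above 0.99.

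The Protocol's symptom-response analysis would count none of these. Some or all might still be filed as unanticipated problems.

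**The case against.** Several points on the other side have force.

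- **A reporting route exists.** Section 7.0 covers problems that are unforeseen or carry risk, including psychological harm, and the Appendix 7 form accepts mild events. A reader might infer that non-entry worsening is counted nowhere; that goes too far. What stands is that the route is discretionary and no score prompts it.
- **The SAP lacks the restriction.** Under the SAP alone, all four scales could be summarised in everyone, and its outcome templates offer ranges and participant counts as well as medians. But none of these is selected, and the Protocol says otherwise. This is a conflict to resolve, and does not cure the gap.
- **The rule is symmetric.** It sets aside non-entry improvement as well as non-entry worsening. Worsening of an entry symptom stays inside the median change, and section 5.0 restricts response analysis without barring safety use. So the documents do not support saying that the rule keeps improvement and drops deterioration. The imbalance comes from the absence of any safety analysis of the scales.
- **Section 4.2 does not say the device disturbs sleep.** It says "Left-ear deviations could be due to discomfort, sleep position, pain at the local site, or infection", as reasons for changing ears. A reader might take this as foreseeing sleep harm, but it does not say that.
- **The SAP's safety and benefit-risk sections are still placeholders.** The missing table may reflect unfinished drafting. That makes now the easy time to add it.

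**Conclusion.** The point holds in limited form. Under the Protocol, scores outside the entry indication(s) enter no planned analysis, and new or worsening non-entry symptoms reach the safety conclusion only through a report that someone chooses to file. Protocol and SAP also conflict on which participants' scores are analysed.

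For a one-symptom participant the unused share is up to 33 of 44 post-baseline scores, assuming weekly packets throughout Weeks 2 to 12. It is smaller for participants with several entry symptoms, which the Protocol's background says is common. How many patients would be affected cannot be derived from the documents: neither the mix of entry symptoms nor a worsening rate is given, and the case counts in the working only indicate scale.

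This is a worthwhile, cheap improvement. It does not invalidate the effectiveness analysis, and it does not show that the device causes harm.

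**What to change.** 1. **Reconcile the documents.** State in both that the stratified populations apply to the effectiveness analyses only.
2. **Add one descriptive table to SAP Section 4.0**, in all participants with at least one device placed, shown by entry stratum. For each of the four scales, give the number and percentage worse than baseline by a stated margin at Weeks 4, 8 and 12, with 95% intervals. Label Week 12 as falling in the no-device period.
3. **Fix the margin and the direction of worsening for each scale before the first (Week 4) interim analysis.** The trial is open-label and interim results are to go regularly to the FDA, so a margin set only at data lock could be chosen with results in view.
4. **Have the risk-benefit conclusion consider this table alongside the reported unanticipated problems.**

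**Cost.** Wording changes and one table from data already collected, with no added visits or questionnaires. The downside is interpretive: with no control arm, and with participants who start near zero only able to rise, some of the worsening will be ordinary fluctuation. The table should say so and be read as descriptive.

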## **6.0 DATA DISCLOSURE AND SUBJECT CONFIDENTIALITY**

Medical record confidentiality and data protection will be maintained at every visit. Subject medical information obtained as a result of this study is considered confidential and disclosure to third parties, other than those noted below, is prohibited. Data generated during this study is to be available for inspection on request by the FDA or other government regulatory agency auditors, the Sponsor's authorized representatives, and the IRB.

## **7.0 ADVERSE EVENT(S)**

Potential unanticipated problems require prompt reporting to the central IRB and study sponsor. These problems potentially place subjects or others at greater risk of physical or psychological harm than was previously recognized, and warrant consideration of substantive changes in the protocol or informed consent process or other action in order to protect the safety, welfare, or rights of participants. The central IRB must be notified within 5 calendar days of the event and the study sponsor within 24 hours. The completed IRB Unanticipated Problem Form (Appendix 7) must be received by the central IRB within 10 calendar days of the event to avoid a major deviation.

Unanticipated problems are defined as those problems which alter the risks to subjects or others. This includes any study suspensions or holds. This form will be used to report any problem that is unforeseen or involves risk. One form will be used per event or problem.

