#### 4.1 Phase I Study Assessment Tables

Nu-Life Solutions Miniaturized Wearable Medical Technology - Nu-V3		Study Treatment Assessments Table										Nu-V3
		*Evaluations are completed weekly, every 7 days =3 days										
Evaluation*	Study Treatment											
	Week 1	Week 2	Week 3	Week 4	Week 5	Week 6	Week 7	Week 8	Week 9-11	Week 12		
Informed Consent	x											
Inclusion and Exclusion 	x											
Patient Registration 	x											
Medications Form 	x			x				x		x		
Patient Onboarding and Orientation 	x											
In office assessment	x	x	x	x	x	x	x	x		x		
New Device Placed	x		x		x		x					
Pad Replaced		x		x		x		x				
Treatment Forms 	x	x	x	x	x	x	x	x				
No Device									x	x		
ePRO Questionnaires 	x	x	x	x	x	x	x	x	x	x		
Patients' Global Impression of Change ePRO form (PGIC) 		x	x	x	x	x	x	x		x		
Providers' Global Impression of Change ePRO form (PGIC)		x	x	x	x	x	x	x		x		
Family Global Impression of Change ePRO form (PGIC)		x	x	x	x	x	x	x		x		
Optional Patient Media Testimony	x			x				x		x		

1. Inclusion/Exclusion, Registration, Medications, Treatment forms to be completed by site coordinator via online module.  
 2. Patient Onboarding and Orientation includes introductory demographics form, Nu-V3 patient training video  
 3. ePRO questionnaires completed on patient's mobile device: DQ-9 (baseline), PTB-7, PEG, GAD-7, PHQ-9, PROMIS 4a, PGIC  
 4. If patient consents to media testimony, site will collect via study collection process every 4 weeks.

Evaluation*	Post Study Intervention Assessments Table														
	*Evaluations are completed weekly, every 7 days ±3 days														
	Optional Maintenance Therapy										Long Term Follow Up				
Week 13	Week 14	Week 15-16	Week 17	Week 18	Week 19-20	Week 21	Week 22	Week 23	Week 24	Week 25	Week 26	Week 27-28	Week 29	Weeks 30-31	Week 32
Medications Form 				x			x			x					x
In office assessment	x	x		x	x		x	x							
New Device Placed	x			x			x								
Pad Replaced		x			x			x							
Treatment Forms 	x	x		x	x		x	x							
No Device			x			x			x	x	x	x	x	x	x
ePRO Questionnaires 	x	x		x	x		x	x	x	x		x			x
Patients' Global Impression of Change ePRO form (PGIC) 	x	x		x	x		x	x				X			X
Providers' Global Impression of Change ePRO form (PGIC)		x			x			x				X			X
Family Global Impression of Change ePRO form (PGIC)		x			x			x				X			X
Optional Patient Media Testimony		x			x			x				x			X

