Risks to Health: Potential unanticipated problems require prompt reporting to Aspire IRB. These problems potentially place subjects or others at greater risk of physical or psychological harm than was previously recognized, and warrant consideration of substantive changes in the protocol or informed consent process or other action in order to protect the safety, welfare, or rights of participants. Aspire IRB must be notified within 5 calendar days of the event. The completed IRB Unanticipated Problem form (Appendix 3) must be received by Aspire IRB within 10 calendar days of the event. Unanticipated problems are defined as those problems which alter the risks to subjects or others. This includes any study suspensions or holds. This form will be used to report any problem that is unforeseen or involves risk. One form will be used per event or problem.

Table 4.1: Unanticipated Problems Involving Risk to Patients or Others			
	Phase I	Phase II	Total
UPIRTSO 1 (number)			
UPIRTSO 2 (number)			
UPIRTSO 3 (number)			
Overall UPIRTSOs Reported			

Table 4.2: Risk/ Mitigation Measures	
Identified Risk	Mitigation Measures

Insert Safety Analysis Here

Section 5.0: Results

Results: The principal safety and effectiveness results from patients in the Nu-V3 study are provided below. The primary safety analysis was based on all patients registered and included all reported UPIRTSO events. The primary safety endpoint included imputation for missing clinical outcomes data using the logistic regression method. The imputation model included baseline characteristics including age, sex/gender, marital status, primary language spoken, race/ethnicity, education history, and veteran status.

Primary Safety Endpoint:

Insert Primary Safety Endpoint Statistical Analysis

Insert Primary Safety Endpoint Statistical Table

Primary Effectiveness Endpoint:

Insert Primary Effectiveness Endpoint Statistical Analysis

Insert Primary Effectiveness Endpoint Statistical Table- 8 weeks

Secondary Effectiveness Endpoint:

Insert Primary Effectiveness Endpoint Statistical Analysis

Insert Primary Effectiveness Endpoint Statistical Table: 4, 8, 12 weeks

Sub-Analyses:

Insert Sub-Analyses Statistical Analysis

Insert Sub-Analyses Statistical Tables

Special Controls:

Insert Special Control Section Here

Benefit/Risk Determination:

Insert Benefit/Risk Section Here

Section 5.0: Administrative Information

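### IRB reporting limits run from the event rather than from site awareness, so an event from the first 18 days of the 28-day gap after Week 8 that surfaces only at Week 12 cannot be filed on time

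*Protocol*

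**What the plan says.** **Clocks.** Protocol section 7.0 states: "The central IRB must be notified within 5 calendar days of the event and the study sponsor within 24 hours". The completed Unanticipated Problem Form "must be received by the central IRB within 10 calendar days of the event to avoid a major deviation". Only this 10-day limit carries the label of a major deviation. The 24-hour sponsor notice has no start point of its own. SAP Section 4.0, under Risks to Health, repeats the rule: "Aspire IRB must be notified within 5 calendar days of the event", with the form due by day 10. The SAP omits the 24-hour notice and the deviation label. No readable part of either document starts a clock at the moment the site learns of the event.

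**Contacts.** In the protocol's section 4.1 table, the row "In office assessment" is ticked for Weeks 1 to 8 and for Week 12, and not for Weeks 9-11. Treatment Forms also end at Week 8. ePRO continues through Weeks 9-11, and the table footnote lists its content: "ePRO questionnaires completed on patient's mobile device: DQ-9 (baseline), PTB-7, PEG, GAD-7, PHQ-9, PROMIS 4a, PGIC".

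**Endpoint.** Section 8.1: "The primary safety endpoint is the occurrence of reported unanticipated problems involving risk to subjects or others".

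**Form.** Appendix 7 has an onset date and a dated initial report, but no field for when the site became aware.

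**The concern.** A reporting limit should be one that a careful site can always meet. Counting from the event works if the site hears of it at once. It fails if the event comes to light at a scheduled visit and the visits are further apart than the limit. Section 4.0 describes the in-person session as the time when staff check for device effects, and after Week 8 no such session takes place until Week 12.

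The gap is not wholly off treatment. The device placed at Week 7 lasts up to 14 days and its pads are changed at Week 8, so roughly the first week of the gap is the last week on device.

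Two things are at stake. First, the plan labels as a major deviation something the site could not have prevented, and without an awareness date on the form nobody can separate late discovery from slow reporting. Second, the primary safety endpoint consists of reported problems, so a stretch of follow-up in which nothing readable asks patients about new health events weakens capture for that endpoint.

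**Working it through.** The plan gives no figure of its own on this point, so there is none to reproduce. The check is date arithmetic.

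**Inputs**
- Limits of 5 and 10 calendar days from the event: protocol section 7.0 and SAP Section 4.0.
- Visits at Weeks 1 to 8 and Week 12: protocol section 4.1. Week 8 to Week 12 is 4 × 7 = 28 days.
- Window of 3 days either side of each visit: section 4.1. The sign is garbled in the extracted main table but reads ± in the maintenance table. With a window at each end, the gap runs from 28 − 6 = 22 to 28 + 6 = 34 days, and a weekly interval can stretch to 7 + 6 = 13 days.

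**Assumptions (mine, not the plan's):** onset is spread evenly over the interval, and the site first learns of the event at the next visit.

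**Formula:** share already late at discovery = (gap − limit) / gap, or zero if the limit is at least as long as the gap.

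| Interval | Days | Past 5-day notice | Past 10-day form limit |
|---|---|---|---|
| Week 8 to 12, nominal | 28 | 23/28 = 82% | 18/28 = 64% |
| Week 8 to 12, shortest | 22 | 17/22 = 77% | 12/22 = 55% |
| Week 8 to 12, longest | 34 | 29/34 = 85% | 24/34 = 71% |
| Weekly visits, nominal | 7 | 2/7 = 29% | 0/7 = 0% |
| Weekly visits, longest | 13 | 8/13 = 62% | 3/13 = 23% |

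I give no share for the 24-hour sponsor notice, because the text does not say when it starts.

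**Whole main study.** Weeks 1 to 12 contain seven 7-day intervals and one of 28 days, 77 days in all. Under the same assumptions 18/77 = 23% of event days miss the 10-day limit, and all 18 lie in the gap after Week 8.

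**Observation period.** Protocol section 4.0 gives 4 weeks of observation after treatment; the SAP's design summary gives 2, although the SAP's own table runs to Week 12. If a 2-week period meant a visit 14 days after Week 8, the share past 10 days would be 4/14 = 29%. The size of the problem therefore depends on a point on which the documents disagree.

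**Could ePRO close the gap?** The readable questionnaires in Appendix 11 have two items that touch on safety: PTB-7 item 3 (discomfort that made the patient adjust the device) and PHQ-9 item 9 (thoughts of death or self-harm). Neither would reveal a hospital admission or a faint.

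**After the change.** With the clock started at site awareness, 0 of 28 event days are late merely because the event was found at Week 12.

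**The case against.** Several points on the other side are sound.

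- **Not every late discovery is a deviation.** A reader might infer that any event found at the next visit is already a major deviation. The text does not support that. The label attaches only to the form arriving after day 10. Events in the last 10 days of the gap (10/28 = 36%) can still be filed in time, and with nominal weekly visits no event is past day 10.
- **Deterrence is an inference.** A reader might also conclude that sites are discouraged from filing. Nothing in the documents says so, and a form that is never filed misses the limit too. The rule may deter late reports, because the breach becomes visible once someone files, but this is a judgement about behaviour.
- **The endpoint does not drop late reports.** SAP Section 5.0 includes every reported event in the safety analysis. Lateness creates a deviation, not an exclusion.
- **Patients are not out of contact.** They complete ePRO in Weeks 9-11 and may call the site. The percentages apply only to events that first surface at a visit.
- **Some material could not be seen.** The Weeks 9-12 process map and the consent pages are unavailable. They may give patients reporting instructions, so it cannot be said that no route exists.
- **The limits may be the central IRB's own.** The documents do not say whose rule they are, so the sponsor may not be free to reword them.

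These points narrow the claim. They leave two things standing: the readable rule cannot be met for part of follow-up, and the readable Weeks 9-11 forms ask no general question about new health problems.

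**Conclusion.** The point holds within limits. For an event that surfaces only at Week 12, 64% of onset days in the nominal 28-day gap (55-71% with the windows) already lie beyond the 10-day form limit and give an unavoidable major deviation. For 82% (77-85%) the 5-day notice has also passed, which the protocol does not label a deviation. Between nominal weekly visits the figures are 29% and zero. All rest on even onset and no earlier contact; prompt reports by patients reduce the problem directly.

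The documents do not support the stronger readings that all events found late are major deviations, that sites are discouraged from filing, or that late reports are lost from the endpoint. The case for change is that the rule cannot always be met as written, that discovery cannot be told apart from delay, and that capture of a primary endpoint of reported problems can be improved cheaply. The maintenance table also shows no office visits after Week 22, but it may be damaged in extraction and the main case does not depend on it.

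**What to change.** - In protocol section 7.0 and SAP Section 4.0, start every clock when the site becomes aware of the event, and give the 24-hour sponsor notice an explicit start point. Check first against the central IRB's own reporting rule.
- Add an awareness date to the Appendix 7 form beside the existing onset and report dates.
- Add one yes/no item to the ePRO packets for Weeks 9-11 and long-term follow-up, asking about any new health problem or hospital visit since the last questionnaire, with a positive answer routed to the site.
- Reconcile the 4-week observation period in protocol section 4.0 with the 2-week period in the SAP's design summary.

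The cost is some rewording, one date field and one questionnaire item. The downside is a few more reports to process.
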